## ABSTRACT

### **Title: A Pilot Study of Oral Calcitriol in Patients at High Risk for Lung Cancer**

**Sponsor:** NCI

**Phase:**

#### **Primary Objectives**

To determine the toxicity profile of an oral dose of calcitriol 45 mcg every other week (QOW) in patients at high risk of lung cancer.

**Overview of the Study Design:** The FDA has requested that a toxicity trial of calcitriol be completed in subjects without cancer using a 45 mcg dose at a lower frequency than was proposed in the previously approved Phase II lung cancer prevention trial. The FDA concerns focus on the lack of evidence of the safety of calcitriol in "healthy" patients who do not have cancer. However, the high risk lung cancer cohort at RPCI is comprised of patients with moderate to severe COPD. In order to document both the toxicity profile of calcitriol at this dose and frequency in high risk subject we have designed a Pilot study. This design incorporates a single-arm toxicity study of 20 patients.

In the proposed "Pilot single-armed pilot study" of 45 mcg of calcitriol, PO, QOW, dosing will continue for 3-months with a defined toxicity monitoring schedule outlined below. A total of 40 patients will be recruited from the High Risk Lung Cancer Screening Clinic and once screened and consented; they will be assigned to calcitriol (n=40). Once 20 patients on calcitriol have completed the 3-month treatment, an interim analysis of adverse events will be performed. Specific criteria for early stopping are outlined below. If the DSMB review of the interim analysis supports proceeding, the remaining 20 patients will be recruited into the trial. A follow-up bronchoscopy will be performed on all subjects after the end of the intervention period according to their routine follow-up schedule.

#### **Eligibility Criteria:**

##### **Inclusion Criteria**

1. Must have pathologically confirmed squamous metaplasia or squamous dysplasia documented by autofluorescence bronchoscopy within the preceding 60 months.
2. Must be a former or current smoker.
3. Must be between the ages of 40-79 years.
4. Participants must have a total granulocyte count of  $> 1.5 \times 10^9/L$ , and a platelet count of  $> 100 \times 10^9/L$ .
5. Participants must have adequate renal function with a calculated creatinine clearance of  $> 60 \text{ ml/min}$  with a serum specimen collection at baseline using the Cockcroft-Gault formula:  
$$eCr = \frac{(140 - \text{Age}) \times \text{Mass (in kilograms)} \times [0.85 \text{ if Female}]}{72 \times \text{Serum Creatinine (in mg/dL)}}$$
6. Participants must have a 24-hour calcium concentration that is  $\leq 300 \text{ mg/24 hours}$  as measured in a 24-hour urine collection at baseline.

I 90206 Amendment # 18

7. Participants must have a total bilirubin less than the upper limit of normal and transaminases/alkaline phosphatase  $\leq 2.5 \times$  IULN.
8. Participants must have an albumin of  $\geq 2.5$  g/dl.
9. Participants must have an ionized serum calcium within normal limits.
10. Must meet ECOG performance status criteria of 0-1 (0 = fully active, must be able to carry out all pre-disease activities without restriction; 1 = restricted in physically strenuous activity, but ambulatory and able to carry out work of a light or sedentary nature).
11. Must be willing to attend all scheduled study visits, complete all study questionnaires, and allow biological specimen collection including a bronchoscopy within 3-4 months after enrollment into the study
12. Women of child-bearing potential (i.e. women who are pre-menopausal or not surgically sterile) must use acceptable contraceptive methods (abstinence, intrauterine device (IUD), oral contraceptives or double barrier device) and must have a negative serum or urine pregnancy test within 1 week prior to beginning treatment on this trial. Sexually active men must also use acceptable contraceptive methods. Pregnant or nursing patients are excluded from participating in this trial. Contraceptive use needs to be continued at least 1 month after the trial has ended.
13. Must be able and willing to sign an informed consent approved by the Institutional Review Board (IRB).

### **Exclusion Criteria**

1. Subjects with life-threatening medical conditions that would preclude bronchoscopy, including: acute cardiac failure, which is unstable despite medication use; uncontrolled hypertension; uncontrolled diabetes mellitus; or unstable coronary artery disease.
2. Patients with severe metabolic disorders that would preclude administration of calcitriol.
3. Evidence of current disease with lung cancer or head and neck cancer.
4. Patients may have a prior history of lung cancer or head and neck cancer treated with curative intent, provided that there has been no evidence of disease (NED) for  $> 1$  year. The qualifying AF bronchoscopy must be negative for malignancy.
5. Patients with a history of any other malignancy within 3 years except non-melanoma skin cancer or cervical CIS.
6. Patients with a history of renal lithiasis within the last 5 years or patients with evidence of kidney stones on entry evaluation.
7. Patients with impaired renal function CRCL  $\leq 60$  mL/min.
8. Patients with hypercalcemia (using ionized calcium).
9. Subjects taking calcium supplements. If subjects are willing to discontinue these supplements, there must be a two-month wash out period before enrollment.
10. If patients are routinely taking a multivitamin supplement, they will be asked to continue the supplement as long as the amount of Calcium and vitamin D in the supplement is not in excess of the RDA (recommended daily allowance). If they are not taking a multivitamin supplement, they will be asked to not start supplementation while on study.
11. Subjects with a known hypersensitivity to calcitriol.
12. Subjects taking thiazides (which can decrease urinary excretion of calcium)
13. Patients taking phenobarbital, digitalis, thiazides or ketoconazole.

I 90206 Amendment # 18

14. Patients taking digoxin or patients who are susceptible to calcium-related dysrhythmias.
15. Patients taking bile acid binding drugs (such as cholestyramine and colestipol).
16. Patients taking Danazol.
17. Patients taking aluminum-based antacids.
18. Oral ketoconazole or other azole antifungals.
19. Women who are pregnant or lactating are excluded from the study.
20. No known allergies to tree nuts (i.e. almonds).

**Target Study/Duration:** A total of 40 patients will be recruited. The intervention is planned for 3 months and the total duration of the study is expected to last 11 years.

**Patient Population:** Male or female patients at least 40 years old and younger than 80 years old, former and current smokers, who on a previous bronchoscopy had at least one metaplasia or dysplasia diagnosed, who do not have lung cancer and who are eligible for a second bronchoscopy.

[figure not shown]
**Primary Endpoints:**

To determine the number of patients with Grade III-IV toxicities or any Grade II toxicities *that last more than two weeks* associated with a 45 mcg dose of calcitriol administered every other week (QOW) in this population of patients at high risk of lung cancer.

**Brief Statistical Section:**

We will test the null hypothesis that the proportion of grade 3-4 toxicities and grade 2 toxicities lasting more than 2 weeks will be 10% versus the one-sided alternative that the proportion of grade 3-4 toxicities will be greater than 10%. Given a sample size of n=40, assuming an alpha level 0.05, we will have 80% power to detect the proportion of toxicities of 15% or larger. An interim analysis will be performed after the first 20 subjects on calcitriol have completed the study. The study can be stopped early if the requirements of the null hypothesis (that this dose of calcitriol dose not result in an excess of DLT reports) are met that  $\leq 1$  toxicity is observed. After a full review of the data is completed by the DSMB the results will be reported to the FDA. Otherwise, the remaining 20 subjects on calcitriol will be recruited and treated at the end of the study period (3 months), at which point we will either reject the null hypothesis (if 8 or more toxicities are observed) or not reject the null hypothesis if 7 or less toxicities are observed.

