## 1. BACKGROUND

The primary aim of this proposal is to establish the safety of calcitriol in this population of high risk lung cancer patients, who do not have cancer. With the safety data generated from this trial, these investigators will be able to proceed with a double-blind placebo controlled clinical trial of 45 mcg of calcitriol QW, as previously approved.

**Occurrence of Lung Cancer:** Lung cancer is the leading cause of cancer death in the United States, and is a massive public health problem worldwide. It is estimated that 1.2 million people are diagnosed with lung cancer on an annual basis (1). Although there is clinical evidence that the survival of lung cancer dramatically improves with the diagnosis of disease at earlier stages (2-5) and the staging system for lung cancer is based on this relationship (6), the overwhelming majority of lung cancer patients have advanced stage disease at the time of diagnosis. The 5-year survival for lung cancer is only 15%, despite the integration of new chemotherapy agents into surgical and radiotherapy treatment (1).

**Target Population for Lung Cancer** The increase in lung cancer since 1923 is directly related to cigarette smoking (7). At present, approximately 25% of the US adult population smokes, and 40-50 million Americans are former smokers. Although reduction of cigarette smoking will be helpful to reduce lung cancer incidence, the risk of developing lung cancer for former smokers does not decay for decades after smoking cessation (8, 9). Smokers who develop chronic obstructive lung disease (COPD) have additional risk for the development of lung cancer (10-12). The relative risk of lung cancer in individuals with high levels of exposure to asbestos is 15:1 and the observed risk for those with both tobacco and asbestos exposure is dramatically higher (13). Prior aerodigestive tract cancers may also be thought of as risk factor for the development of a second primary lung cancer (14-16). Patients who are current or former smokers with multiple risk factors including COPD, asbestos exposure, or prior aerodigestive tract cancer are at high risk for lung cancer, and are the most likely to benefit from early detection strategies,(17) and ultimately from chemoprevention interventions (18).

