**Optimal Biologic Concentration Determination** - The optimal biologic concentration will be defined as the steady state concentration range that is associated with less than grade 2 toxicity and leads to target inhibition in 90% or greater of patients. Because there are inter-individual variations in absorption and metabolism of calcitriol, a more rational approach will be to evaluate the feasibility of relating concentrations of calcitriol rather than administered dose, to pharmacodynamic markers and toxicity. Thus, we will examine the relationship between exposure levels (Cp or AUC) of calcitriol with pharmacodynamic endpoints and polymorphisms in CYP24A1 and calcitriol metabolizing enzymes. Determining the strength and direction of the association between genotype(s), PD endpoints and calcitriol exposure levels will allow the construction of a preliminary model that will allow personalized dosing to a target drug exposure range (Cp or AUC) for validation in future chemoprevention studies. Based on these data, patients could be initially started on therapy on a non-toxic median dose that leads to target exposure levels. Eventually, doses could be adjusted during treatment to reach target concentrations, as is done with other drugs that have narrow therapeutic indexes such as vancomycin and busulfan for bone marrow transplantation.

We will test the null hypothesis that the proportion of grade 3-4 toxicities or grade 2 toxicities that persist more than two weeks will be 10% versus the one-sided alternative that the proportion of these toxicities will be greater than 10%. An interim analysis will be performed after the first 20 subjects on calcitriol have completed the study. The study can be stopped early at the interim point and the null hypothesis will not be rejected if  $\leq 1$  toxicity is observed, at which time the DSMB will summarize the findings and the results, including all toxicity reports will be submitted to the FDA. Otherwise, the full 40 subjects will be recruited into the study. At the end of the study period, we will again either reject the null hypothesis (if 8 or more DLT toxicities are observed) or not reject the null hypothesis if 7 or less toxicities are observed.

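### The trial aims to establish safety, but its only favourable test result is non-rejection of a 10% rate; no upper confidence limit is planned, and by the exact limit neither count that allows the interim stop excludes rates above 10%

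*Combined protocol and SAP*

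**What the plan says.** Section 1 (Background) states the purpose: "The primary aim of this proposal is to establish the safety of calcitriol in this population of high risk lung cancer patients". The first primary objective in Section 3 (Methods) says the same for this dose in patients without cancer. The abstract is more descriptive. Its objective is to determine a toxicity profile, and its primary endpoint is a count of patients: "To determine the number of patients with Grade III-IV toxicities or any Grade II toxicities", the latter if they last more than two weeks.

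One test addresses this endpoint. The null is a 10% rate and the one-sided alternative is a higher rate, with 40 patients and alpha 0.05. After 20 patients the study may stop if 1 or fewer toxicities have been seen. At 40 patients the null is rejected with 8 or more.

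The meaning of the interim stop is worded in two ways:

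- Abstract, Brief Statistical Section: the study can stop if the "requirements of the null hypothesis (that this dose of calcitriol dose not result in an excess of DLT reports) are met", tied to 1 or fewer toxicities.
- Section 12 (Statistical Analysis): "The study can be stopped early at the interim point and the null hypothesis will not be rejected if" 1 or fewer are observed.

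At 40 patients both sections say only that they will "not reject the null hypothesis if 7 or less toxicities are observed". Neither section plans a confidence interval or upper limit for the toxicity rate. The stop is permissive in both, and the abstract's design overview adds a review step: "If the DSMB review of the interim analysis supports proceeding, the remaining 20 patients will be recruited into the trial".

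**The concern.** Failing to reject a 10% rate does not show that the rate is 10% or less, least of all with 20 patients. The abstract's clause reads as if a low interim count confirms a null of no excess. Section 12 gives the same count its proper, weaker meaning.

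The difference matters because of how the result will be used. The findings go to the FDA, which asked for safety evidence in people without cancer, and Section 1 expects them to open the way to a placebo-controlled trial. If 1/20 is taken as no excess, the reader has no planned figure showing which rates remain compatible with the data. The descriptive objective has the same gap, because a toxicity rate from 20 or 40 patients would be reported without stated precision.

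**Working it through.** **Inputs.** From the abstract and Section 12: null rate 10%, one-sided test, alpha 0.05, interim at 20 patients with a stop at 1 or fewer, final rejection at 8 or more of 40. Each count is taken as a number of patients, as in the primary endpoint, and patients are treated as independent with a common rate p.

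**The plan's own figures.** With X binomial(40, 0.10), P(X ≥ 8) = 0.0419, or 0.0412 allowing for the interim stop. The cut-off therefore agrees with alpha 0.05. The stated 80% power at a true rate of 15% does not reproduce: P(X ≥ 8) at p = 0.15 is 24.4%, or 24.1% with the interim stop. That is a separate error and adds no weight here.

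**Exact (Clopper-Pearson) one-sided 95% upper limits.** The limit U for x of n solves P(X ≤ x | n, U) = 0.05.

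- 0/20: (1 − U)^20 = 0.05, so U = 1 − 0.05^(1/20) = 1 − 0.8609 = 13.9%.
- 1/20: (1 − U)^20 + 20U(1 − U)^19 = 0.05. At U = 0.2161 the terms are 0.0077 + 0.0423 = 0.0500, so U = 21.6%.
- 6/40: U = 27.5%.
- 7/40: U = 30.4%.

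Both counts that allow the interim stop have limits above 10%.

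**Dependence on method (one-sided 95% upper limit).**

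| Count | Exact | Wilson | Mid-p | Jeffreys |
|---|---|---|---|---|
| 0/20 | 13.9% | 11.9% | 10.9% | 9.0% |
| 1/20 | 21.6% | 19.6% | 18.9% | 18.0% |

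At 0/20 one method falls just below 10%. At 1/20 none is near it.

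**How often higher true rates give a stopping count.** P(X ≤ 1 | 20, p) = (1 − p)^20 + 20p(1 − p)^19.

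- p = 0.10: 0.1216 + 0.2702 = 39.2%
- p = 0.15: 0.0388 + 0.1368 = 17.6%
- p = 0.20: 0.0115 + 0.0576 = 6.9%

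**Effect of the interim stop on the limit.** The ordinary exact limit ignores the interim look. Suppose the stop is always taken and p = 0.2165, just above the limit for 1/20. The limit then misses p in two ways:

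- The study stops at 0 or 1 of 20, probability 0.0496.
- It continues and ends with 4 or fewer of 40 (the limit at 4/40 is 21.4%), probability 0.0283.

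Coverage is 1 − 0.0496 − 0.0283 = 92.2%, the minimum found over a grid of p. If the stop is never taken, the minimum is 95.0%.

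A stage-wise limit solves P(X1 ≤ 1) + P(X1 ≥ 2, total ≤ x) = 0.05, where X1 is the interim count. It keeps at least 95% coverage when the stop is always taken. It gives 30.6% at 7/40, against 30.4%, but 21.7% at 2/40, against 14.9%.

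**The case against.** The best reply is that this is one badly formed clause in an abstract. It can be read as saying that the stopping requirement is met, with the bracket merely explaining the null. Section 12, the fuller text, words the same rule correctly, and at 40 patients both sections claim only non-rejection. The DSMB reviews the data, and the FDA receives the counts and all toxicity reports, so nobody has to rely on the clause. All of this stands, and it limits the harm. It does not supply the missing limit, which is needed whichever way the clause is read.

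Three stronger readings are tempting, and the documents do not support them:

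- A reader might infer that the sponsor will report an interim stop as proof of safety. No section says so; what follows a stop is DSMB review and a report to the FDA.
- A reader might infer that a conclusion of no excess at 1/20 would be wrong. The observed rate there is 1/20 = 5%, and at a true rate of 20% the study would pass the stopping count in about 93% of trials (1 − 0.069). The conclusion would be unsupported, not shown to be false.
- A reader might infer that no analysis of 0/20 could exclude 10%. That holds for the exact limit, and for Wilson and mid-p, but not for Jeffreys.

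It can also be said that an elaborate interim-adjusted interval is too much for a 40-patient pilot. That is fair: an ordinary exact limit with a note on its coverage is enough.

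**Conclusion.** The point holds and should be fixed. The aim is to establish safety, yet the plan's only favourable test outcome is non-rejection, and it provides no measure of the rates that the data leave open. By the exact limit, a stop at 0/20 leaves rates up to 13.9% compatible with the data, and a stop at 1/20 leaves rates up to 21.6%. The 1/20 result is secure across methods; the 0/20 result depends on the method chosen. A final count of 7/40, which is not rejected, leaves rates up to 30.4%. The figures assume one count per patient and independent patients with a common rate. The fault in wording is confined to the abstract's interim clause; the missing limit affects both statistical sections.

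**What to change.** 1. In the Brief Statistical Section, replace the clause saying that the null's requirements are met with Section 12's statement that the null hypothesis will not be rejected. Add one sentence: non-rejection will not be interpreted as evidence of safety.

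2. In the Brief Statistical Section and Section 12, plan to report the proportion of patients with a qualifying toxicity, in the unit of the primary endpoint, with an exact (Clopper-Pearson) one-sided 95% upper limit U. Report it at the interim if the study stops there, otherwise at 40 patients. Describe safety as rates above U% being excluded.

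3. Note beside the limit that, because the interim stop is optional, coverage can fall to about 92% if the stop is always taken. If the stop is made binding, a stage-wise limit may be used instead, at the price of wider limits at low final counts.

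The cost is a few sentences and one confidence limit. Enrolment, data collection, the interim rule and the 7/8 cut-off do not change. The downside for the sponsor is that final counts of 6 or 7 of 40, although not rejected, would carry limits of about 27% to 30% and could not be described as no excess.

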**STUDY SCHEMA**

I 90206 Amendment # 18

## 1. BACKGROUND

The primary aim of this proposal is to establish the safety of calcitriol in this population of high risk lung cancer patients, who do not have cancer. With the safety data generated from this trial, these investigators will be able to proceed with a double-blind placebo controlled clinical trial of 45 mcg of calcitriol QW, as previously approved.

**Occurrence of Lung Cancer:** Lung cancer is the leading cause of cancer death in the United States, and is a massive public health problem worldwide. It is estimated that 1.2 million people are diagnosed with lung cancer on an annual basis (1). Although there is clinical evidence that the survival of lung cancer dramatically improves with the diagnosis of disease at earlier stages (2-5) and the staging system for lung cancer is based on this relationship (6), the overwhelming majority of lung cancer patients have advanced stage disease at the time of diagnosis. The 5-year survival for lung cancer is only 15%, despite the integration of new chemotherapy agents into surgical and radiotherapy treatment (1).

**Target Population for Lung Cancer** The increase in lung cancer since 1923 is directly related to cigarette smoking (7). At present, approximately 25% of the US adult population smokes, and 40-50 million Americans are former smokers. Although reduction of cigarette smoking will be helpful to reduce lung cancer incidence, the risk of developing lung cancer for former smokers does not decay for decades after smoking cessation (8, 9). Smokers who develop chronic obstructive lung disease (COPD) have additional risk for the development of lung cancer (10-12). The relative risk of lung cancer in individuals with high levels of exposure to asbestos is 15:1 and the observed risk for those with both tobacco and asbestos exposure is dramatically higher (13). Prior aerodigestive tract cancers may also be thought of as risk factor for the development of a second primary lung cancer (14-16). Patients who are current or former smokers with multiple risk factors including COPD, asbestos exposure, or prior aerodigestive tract cancer are at high risk for lung cancer, and are the most likely to benefit from early detection strategies,(17) and ultimately from chemoprevention interventions (18).

**Chemoprevention Trials in Lung Cancer:** Primary chemoprevention trials have examined the use of vitamin E and vitamin A (19, 20), which failed to demonstrate benefit in the prevention of lung cancer in smokers. *Tertiary chemoprevention* trials are aimed at the prevention of second primary cancers in individuals who have been previously treated for cancer showed that 13-cis-retinoic acid (isotretinoin) seemed to prevent second primary tumors in resected head and neck cancer patients (21) and retinol palmitate reduced second primary tumors in patients with resected lung cancer. (22). A large randomized follow up study by EUROSCAN failed to confirm benefit from retinol palmitate in the prevention of second primary lung cancers (23). In a subsequent NCI multicenter Phase III placebo-controlled, randomized trial of isotretinoin, the rate of second primary tumors, recurrences, and mortality were not reduced in 1166 patients with Non-Small Cell Lung Cancer (NSCLC)(24). Furthermore, secondary multivariate and subset analyses suggested that isotretinoin was in fact harmful in current smokers and beneficial only in never smokers. Primary and tertiary chemoprevention trials are typically large randomized phase III efforts that require expenditure of considerable resources, and it is reasonable to propose that candidate chemoprevention agents first show activity on a smaller scale. Lee conducted a secondary chemoprevention trial in 152 smokers with biopsy-confirmed metaplasia or dysplasia of the lung epithelium, and found that isotretinoin (13-cRA) (I

I 90206 Amendment # 18

mg/kg) did not cause regression of the lesion when compared to placebo (25). A summary of secondary chemoprevention trials for lung cancer is shown in Table 1.

In a more recent study from the same institution (26) 9-cis-retinoic acid (RA) was compared with 13-cRA plus  $\alpha$ -tocopherol, or placebo. This group of 226 former smokers were randomly assigned to treatment groups and re-evaluated in 3 months. Six biopsies from predetermined sites were evaluated. The results showed that while neither treatment affected that histology of the sites, 9-cis-RA did restore the RAR $\beta$  (retinoic acid receptor) in a significant number of lesions. Another generic difficulty with bronchoscopy-based secondary prevention trials is the possibility that the endobronchial biopsy itself may alter the natural history of metaplasia, or even be “curative” of small areas of dysplasia. Biomarkers are keenly sought as surrogate endpoints for chemoprevention trials (27). On the other hand, it is problematic to find agents that activate biomarkers but fail to reverse intraepithelial premalignant lesions (28, 29). For this reason, it is critical to evaluate biomarkers taken from targeted areas of abnormal epithelial proliferation, as detected by AF bronchoscopy (30).

